3.8. Analysis Visit Windows

Nominal visits will be used for the Pharmacokinetic and Immunogenicity summaries. Details for analysis visit windows used for efficacy and safety analyses in the final analysis can be found [Section 3.8.2](#).

3.8.1. Definition of Key Dates and Study Day

Study Day 1 is defined as the day when the first dose of any study drug was taken, as recorded on the Study Drug Administration eCRF (ie, oral LEN, SC LEN or infusion drugs [GS-5423, GS-2872]).

Last Dose Date is defined as the latest dose date of any study drug as recorded on the Study Drug Administration eCRF (ie, oral LEN, SC LEN or infusion drugs (GS-5423, GS-2872) for participants who prematurely discontinued study drug or completed study drug according to Study Drug Completion eCRF.

Study Days are calculated relative to Study Day 1 of study drug and derived as follows:

- For postdose study days: Assessment Date – First Dose Date + 1
- For days prior to the first dose: Assessment Date – First Dose Date

Baseline Value is defined as the last value obtained on or prior to the first dose of study drug.

Last Study Date is the latest clinic visit dates, and/or the laboratory visit dates, whichever is latest, including the any follow-up visit dates, for participants who prematurely discontinued study or completed study according to the Study Completion eCRF.

Last Exposure Date is defined as follows for participants who prematurely discontinued study or complete study according to Study Completion eCRF (i.e. participant answered “No” or “Yes” for “Did the participant complete the protocol-planned duration of the study” on Study Completion form):

- For participants who receive any injection or infusion, last exposure date is defined as last study date.
- For participants who do not receive any injection or infusion (i.e. for those who only receive oral LEN), last exposure date is defined as the earliest of the last dose date plus 60 days and the last study date.

The last exposure date is defined considering the prolonged exposure of LEN, GS-5423, and GS-2872 after the last dose date of LEN, GS-5423, and GS-2872 through the end of study.

Last Exposure Date of LA Regimen is defined as follows for participants who prematurely discontinued study drug or complete study drug according to Study Drug Completion eCRF (i.e. participant answered “No” or “Yes” for “Did participant complete study drug dosing as specified per protocol” on Study Drug Completion form):

- the earliest date of last study day or ART restart day for participants who prematurely discontinued study or complete study, or

- the ART restart date for participants who were still on study. If the ART restart date is missing, the data cut date will be used to impute the last exposure date for participants who are still on study at the time of the data cut date.

The last exposure date of LA regimen is defined considering the prolonged exposure of LEN, GS-5423, and GS-2872 after the last dose date of LEN, GS-5423, and GS-2872 through the ART restart date.

ART Restart Date is defined as the date when ART is resumed.

3.8.2. Analysis Visit Windows

Analysis Visit Windows Participant visits might not occur on protocol-specified days. Therefore, for the purpose of analysis, observations will be assigned to analysis windows.

The analysis windows for HIV-1 RNA, CD4+ cell count, CD8+ cell count, CD4 %, Hematology, Chemistry, Lipid Panel, Urinalysis, Urine Chemistry, Urine Pregnancy Laboratory Tests, Vital Signs, Weight and ECG are provided in [Table 3-2](#) to [Table 3-4](#).

Table 3-2. Analysis Windows for HIV-1 RNA

Visit ID	Nominal Day	Lower Limit	Upper Limit
Day 1 (Baseline)			1
Week 4	28	2	42
Week 8	56	43	70
Week 12	84	71	98
Week 16	112	99	126
Week 20	140	127	154
Week 24	168	155	175
Week 26	182	176	224
Week 38	266	225	315
Week 52	364	316	413

Table 3-3. Analysis Windows for CD4+ cell count, CD8+ cell count, CD4/CD8 Ratio, Chemistry, Hematology, Urinalysis, Vital Signs, and Weight

Visit ID	Nominal Day	Lower Limit	Upper Limit
Day 1 (Baseline)			1
Week 4	28	2	56
Week 12	84	57	133
Week 26	182	134	224
Week 38	266	225	315
Week 52	364	316	413

Table 3-4. Analysis Windows for ECG

Visit ID	Nominal Day	Lower Limit	Upper Limit
Day 1 (Baseline)			1
Week 26	182	2	273
Week 52	364	274	413

For Pharmacokinetic and Immunogenicity analyses, the nominal visit as recorded on the CRF will be used when data are summarized by visit. Any data relating to unscheduled visits will not be assigned to a particular visit or time point and in general will not be included in by-visit summaries. However, the following exceptions will be made:

- An unscheduled visit prior to the first dosing of study drug may be included in the calculation of the baseline value, if applicable.
- For participants who prematurely discontinue from the study, early termination (ET) data will be assigned to what would have been the next scheduled visit where the respective data were scheduled to be collected.

3.8.3. Selection of Data in the Event of Multiple Records in an Analysis Visit Window

Depending on the statistical analysis method, single values may be required for each analysis window. For example, change from baseline by visit usually requires a single value, whereas a time-to-event analysis would not require 1 value per analysis window.

If multiple valid, nonmissing measurements exist in an analysis window, records will be chosen based on the following rules if a single value is needed:

- For baseline, the last nonmissing value on or prior to the first dose date of study drug will be selected, unless specified differently. If there are multiple records with the same time or no time recorded on the same day, the baseline value will be the average of the measurements for continuous data (except for HIV-1 RNA, see below), or the measurement with the lowest severity (eg, normal will be selected over abnormal for safety ECG findings) for categorical data.
- For postbaseline values:
 - The record closest to the nominal day for that visit will be selected with the exception of CD4 cell counts, CD4%, and CD8 cell count in which the latest record will be selected and HIV-1 RNA level (see below).
 - If there are 2 records that are equidistant from the nominal day, the later record will be selected.
 - If there is more than 1 record on the selected day, the average will be taken for continuous data (except for HIV-1 RNA, see below) and the worse severity will be taken for categorical data, unless otherwise specified.
- For baseline HIV-1 RNA, the latest (considering both date and time) record(s) on or prior to the first dose date and time of study drug will be selected.
- For postbaseline HIV-1 RNA, the latest (considering both date and time) record(s) in the window will be selected.
 - If both “HIV RNA COBAS 6800” and “HIV RNA TAQMAN 2.0” are available with the same collection time, the results from the “HIV RNA COBAS 6800” will be selected for analysis purpose.
 - If both “HIV COBAS 6800” and “HIV RNA REPEAT COBAS” (ie, the HIV-1 RNA result obtained from an additional aliquot of the original sample) are available with the same collection time, the results from the “HIV RNA REPEAT COBAS” will be selected for analysis purposes; otherwise, if there are multiple “HIV COBAS 6800” records with the same collection time, the geometric mean will be taken for analysis purposes.
 - If both “HIV RNA TAQMAN 2.0” and “HIV RNA Repeat” are available with the same collection time, the results from the “HIV RNA Repeat” will be selected for analysis purposes; otherwise, if there are multiple “HIV RNA TAQMAN 2.0” records with the same collection time, the geometric mean will be taken for analysis purposes.

If multiple valid nonmissing categorical observations exist in a window, records will be chosen as follows:

- For baseline, the last available record on or prior to the first dose date of study drug will be selected. If there are multiple records with the same time or no time recorded on the same day, the value with the lowest severity will be selected (eg, normal will be selected over abnormal for safety ECG findings).
- For postbaseline visits, the most conservative value within the window will be selected (eg, abnormal will be selected over normal for safety ECG findings).

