Objectives:	
The primary objective of this study is as follows:
 
• To evaluate the safety and tolerability of a combination of the broadly neutralizing antibodies (bNAbs) GS-5423 and GS-2872 (formerly 3BNC117-LS and 10-1074-LS, respectively) in combination with the HIV capsid inhibitor lenacapavir (LEN; GS-6207) 
The secondary objectives of this study are as follows:
 
• To evaluate the efficacy of the study regimens determined by the proportion of participants maintaining virologic suppression (HIV-1 RNA < 50 copies/mL) at Weeks 26• To evaluate the pharmacokinetics (PK) of GS-5423, GS-2872, and LEN• To evaluate immunogenicity of GS-5423 and GS-2872• To evaluate the emergence of resistance to the components of the study regimens 
The exploratory objectives are as follows:
 
• To evaluate changes in HIV reservoir• To evaluate changes in immune biomarkers

Study Design:	
A randomized, blinded, proof-of-concept (POC) study to evaluate the safety and efficacy of a single dose each of a long-acting regimen of LEN, GS-5423, and GS-2872 in adults with HIV-1 infection who are virologically suppressed (HIV-1 RNA < 50 copies/mL) on oral antiretroviral treatment (ART).
 
Participants who provide written consent and meet all eligibility criteria will be randomized in a 1:1 ratio to one of 2 treatment groups based on the dose of GS-2872.
 
Participants will discontinue their background oral antiretroviral (ARV) regimen one day prior to receiving study drugs on Day 1.
 
At Week 26, all participants will resume their background oral ARV baseline regimen (or compatible regimen selected by the investigator) and return to the clinic for visits at Weeks 38 and 52.
 
Unblinded treatment assignments will be provided to the investigators after all participants are back on their baseline ARVs (or compatible regimen selected by the investigator) at Week 26 or have discontinued the study, and the Week 26 analysis has been completed.

Number of Participants Planned:	Approximately 20 in the Primary Cohort, up to 20 in the optional Pilot Cohort

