1.4. Rationale for Dose Selection of GS-5423 and GS-2872

Dose selection for GS-5423 (3BNC117-LS) and GS-2872 (10-1074-LS) in this study is supported by antiviral activity, PK, and safety data from the non-LS forms of each antibody, 3BNC117 and 10-1074, in a Phase 1b proof-of-concept (POC) study in HIV+ participants {[Mendoza 2018](#)}, as well the PK and safety data in healthy volunteers and participants with HIV of the LS forms of each antibody from the ongoing studies, YCO-0946 and YCO-0971.

In the Phase 1b POC study {Mendoza 2018}, MCA-906, the activity of the combination of 3BNC117 and 10-1074 in the setting of ATI was evaluated. In this study, participants who were sensitive to both antibodies (n = 9) maintained viral suppression for a median of 21 weeks after the last dose of the antibodies. An exploratory PK/pharmacodynamic (PD) analysis of these data suggest that in sensitive participants, virologic suppression was maintained when 3BNC117 and 10-1074 concentrations were > 10 µg/mL and > 100 µg/mL, respectively. Virologic breakthrough occurred when the concentrations of the less potent antibody, 3BNC117, fell below 10 µg/mL.

Based on the location of the amino acid substitutions to generate the LS forms of each antibody, as well as delays in time to infection observed in a nonhuman primate disease challenge model (refer to the 3BNC117-LS IB and 10-1074-LS IB), it is anticipated that the 10-1074-LS and 3BNC117-LS antibodies will demonstrate similar antiviral activity to the unmodified forms, at the same target concentrations.

Single doses of GS-5423 and GS-2872 were shown to be safe and well tolerated up to 30 mg/kg in Studies YCO-0946 and YCO-0971. Preliminary PK data from Study YCO-0946 suggest GS-5423 (3BNC117-LS) has a $t_{1/2}$ of approximately 54 days, and IV administration of GS-5423 30 mg/kg is anticipated to maintain concentrations > 10 µg/mL for 26 weeks. Preliminary PK data from Study YCO-0971 suggest GS-2872 (10-1074-LS) has a $t_{1/2}$ of approximately 80 days, and IV administration of GS-2872 10 mg/kg and 30 mg/kg are anticipated to maintain concentrations > 10 µg/mL and > 100 µg/mL, respectively, for 26 weeks.

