6.5. Early Termination

If a participant discontinues their participation prior to Week 26, an Early Termination (ET) visit will be performed.

The following will be performed at the ET visit:

- Review of AEs and changes in concomitant medications
- Complete physical examination
- Weight
- Vital signs (blood pressure, pulse, respiration rate, and temperature)
- Obtain laboratory samples as described in Section 6.7
- Counsel participant regarding the importance of continuing a complete ARV therapy in accordance to standard of care, and refer patient to an appropriate HIV treatment facility

However, if there are any abnormal laboratory results indicating there is a possible or probable causal relationship with the study drug, every attempt should be made to keep the participant in the study and repeat those laboratory tests weekly (or as often as deemed prudent by the investigator) until the abnormality is resolved, returns to baseline, or is otherwise explained.

The participant will be asked to continue attending the scheduled study visits through the Week 52 visit.

- If the participant decides to discontinue the study regimen but continues to attend study visits through Week 52, no other follow-up visits are required.
- If the participant decides to discontinue the study regimen and does not continue to attend study visits through Week 52, the post-ET 30-, 90-, and 180-Day follow-up visits are required. Refer to Section 6.5.1. The post-ET 180-Day follow-up visit may be conducted via a phone call per the investigator's discretion.

Any post-ET 90-Day follow-up visit occurring after the date the Week 52 visit would have occurred may be conducted via a phone call per the investigator's discretion.

If this is not possible or acceptable to the participant or investigator, the participant may be withdrawn from the study.

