- HBV and HCV serology: HBV surface antigen, HBV core antibody, and HBV surface antibody; HCV serology, with reflex to HCV RNA if positive **at screening**
- HIV-1 RNA **at all visits (except Days 2-8)**
- HIV reservoir assay on **Day 1 (predose) and at Week 52**
- Plasma storage samples for virology testing **at all visits (except screening, Days 2-8)**
- Immune biomarker collection on **Day 1 (predose), and at Weeks 4, 26, 38, and 52**

- **PK serum samples for GS-5423 and GS-2872 will be collected in all participants as follows:**

Note: PK samples obtained on Day 1 should be drawn from a separate catheter in the opposite arm from the one used for GS-5423 and GS-2872 IV infusion to avoid contamination.

The exact time of study drug administration and the exact time points (date and time) of collection of plasma samples must be carefully recorded. Serum PK samples for GS-5423 and GS-2872 will be collected at the following time points for all participants:

- Day 1: 0 hour (predose, ≤ 30 minutes prior to dosing of oral LEN for loading), within 5 minutes after the end of the first antibody infusion (GS-5423) and within 5 minutes after the end of the second antibody infusion (GS-2872)
- A single anytime sample at Weeks 4, 8, 12, 16, 20, 24, 26, 38, and 52

In case of ET prior to Week 52, applicable study drug single PK samples will be collected.

- **PK plasma samples for LEN will be collected in all participants as follows:**

PK samples should be drawn from a separate catheter in the opposite arm from the one used for GS-5423 and GS-2872 IV infusion to avoid contamination.

- Day 1: 0 hour (predose, ≤ 30 minutes prior to dosing of oral LEN for loading), within 5 minutes after the end of the first antibody infusion (GS-5423) and within 5 minutes after the end of the second antibody infusion (GS-2872)
- A single anytime sample at Weeks 4, 8, 12, 16, 20, 24, 26, 38, and 52
- In case of ET prior to Week 52, applicable study drug single PK samples will be collected.

- **Optional PK Substudy:**

If participants provide specific separate consent, plasma samples for LEN will be collected at the following times in a subset of participants who will dose in clinic on Day 2 (approximately $n = 14$ evaluable and $n = 7$ from each treatment group):

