8.3. Statistical Analysis Methods

8.3.1. Statistical Analysis of PK Concentration

Individual participant concentration data of LEN, GS-5423, and GS-2872 for participants in the PK analysis set will be listed and summarized using descriptive statistics by treatment group for the primary cohort, the pilot cohort, and for pooled cohorts. In addition, for LEN and GS-5423, individual participant concentration data for participants in the PK analysis set will be summarized for combined treatment groups (total) for the primary cohort, the pilot cohort, and for pooled cohorts. For the LEN PK substudy, individual participant concentration data for PK sample timepoints from Day 1 to Day 8 will be listed and summarized overall (i.e., one summary). Summary statistics (numbers of participants, mean, SD, coefficient of variation [%CV], median, minimum, maximum, Q1, and Q3) will be presented for individual participant concentration data by time point.

Individual concentration data listings and summaries will include all participants with concentration data. If a participant had quantifiable pre-dose, BLQ at end of infusion, or received incorrect dose, the related PK concentration(s) will be captured in the table but will be excluded from the summary statistics, with reasons for exclusion identified. The sample size for each time point will be based on the number of participants with nonmissing concentration data at that time point. For summary statistics, BLQ values will be treated as zero at predose and postdose time points. The number and percentage of participants with concentration BLQ, as well as an indicator if more than one-third of the participants are BLQ, will be presented for each time point. The method to handle BLQ values for PK summaries are described in Section 3.7.2. Concentration values will be presented as received from the bioanalytical lab and summary statistics will be presented to three significant digits.

Participants with viral breakthrough (i.e., HIV-1 RNA \geq 50 copies/mL at Week 26 visit as defined by the FDA-defined snapshot algorithm) will be flagged in the listings.

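### Moving early-termination PK samples forward to the next scheduled visit biases the by-visit antibody concentrations upward, by a small amount up to Week 26

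*SAP*

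**What the plan says.** For PK and immunogenicity, SAP 3.8.2 states that "the nominal visit as recorded on the CRF will be used when data are summarized by visit", and it generally keeps unscheduled data out of by-visit summaries. One exception concerns participants who leave the study prematurely: their "early termination (ET) data will be assigned to what would have been the next scheduled visit where the respective data were scheduled to be collected". The rule looks only at which visit comes next, not at the day of the draw.

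The rule has PK data to act on. Protocol 6.7.1 says: "In case of ET prior to Week 52, applicable study drug single PK samples will be collected". Appendix 2 of the protocol marks PK in the early-termination column and notes that a single sample suffices. The scheduled PK draws are "A single anytime sample at Weeks 4, 8, 12, 16, 20, 24, 26, 38, and 52".

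Under SAP 8.3.1, means, medians, quartiles and extremes "will be presented for individual participant concentration data by time point". The exclusions named there are a quantifiable predose value, a BLQ value at the end of infusion, and an incorrect dose. SAP 3.6.2 lets the pharmacokineticist exclude outliers case by case. Neither provision refers to a relabelled early-termination sample.

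**The concern.** The protocol synopsis describes "a single dose each of a long-acting regimen of LEN, GS-5423, and GS-2872". After the Day 1 infusions the antibody concentrations fall, so an earlier sample is expected to be higher than one taken at the later visit whose label it receives. The error is therefore a bias in one direction rather than noise.

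The by-visit tables and the mean and median plots are where a reader will look to see whether concentrations stay above the targets in Protocol 1.4 for 26 weeks. Those targets are above 10 µg/mL for GS-5423, and for GS-2872 above 10 µg/mL in Treatment Group 1 and above 100 µg/mL in Treatment Group 2. With about 10 participants per group in the Primary Cohort, one value labelled with the wrong time can move a mean or set an extreme.

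**Working it through.** The documents give no figure for the effect of this rule, so there is none to reproduce. The sample-size calculation does not depend on it.

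**Inputs**
- GS-5423 half-life: 54 days (Protocol 1.4) or 62 days (Protocol 1.2.3.2). The protocol gives both, so both are used.
- GS-2872 half-life: 80 days (Protocol 1.2.3.3 and 1.4).
- Gaps between PK visits (Protocol 6.7.1): 28 days up to Week 24, 14 days from Week 24 to 26, 84 days from Week 26 to 38, 98 days from Week 38 to 52.
- Group size: 20 randomized 1:1, so about 10.
- Assumptions: one early-termination participant in the group, since no dropout rate is given; visits on their nominal days; that participant otherwise on the same curve as the rest.

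**Formulas**
- With mono-exponential decline and half-life h, a sample drawn g days before the visit it is labelled with is too high by the factor f = 2^(g/h).
- The visit mean of 10 becomes (9 + f)/10 of its correct value, a rise of (f − 1)/10.

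**Results for a draw one day after the previous visit**

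| Labelled as | g (days) | GS-5423, h = 54 | GS-5423, h = 62 | GS-2872, h = 80 |
|---|---|---|---|---|
| Next 4-weekly visit | 28 − 1 = 27 | 2^(27/54) = 1.41 | 2^(27/62) = 1.35 | 2^(27/80) = 1.26 |
| Week 26 | 14 − 1 = 13 | 2^(13/54) = 1.18 | 2^(13/62) = 1.16 | 2^(13/80) = 1.12 |
| Week 38 | 84 − 1 = 83 | 2.90 | 2.53 | 2.05 |
| Week 52 | 98 − 1 = 97 | 3.47 | 2.96 | 2.32 |

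**Rise in the mean of 10, (f − 1)/10, same column order**
- 4-weekly visit: 4.1%, 3.5%, 2.6%.
- Week 26: 1.8%, 1.6%, 1.2%.
- Week 38: 19.0%, 15.3%, 10.5%.
- Week 52: 24.7%, 19.6%, 13.2%.

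In a combined column of 20 these rises halve.

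**Which rows can occur.** Protocol 6.5 says: "If a participant discontinues their participation prior to Week 26, an Early Termination (ET) visit will be performed". On that wording only the first two rows arise. Protocol 6.7.1 speaks of early termination up to Week 52, which would admit the last two.

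**LEN.** The direction above does not carry over. In Study GS-US-200-4538 the median time to peak after 927 mg SC was 77 days (3 × 1.0 mL) or 84.2 days (2 × 1.5 mL). An early sample may therefore be lower than the value at the later visit.

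**The case against.** The strongest reply is that little depends on this.
- The secondary PK endpoint is PK parameters, and SAP 8.2 computes these from real times whenever possible.
- No test uses the by-visit concentrations. Individual profiles and listings of scheduled against actual draw times are planned (SAP 8.3.1.2), and medians are reported.
- All long-acting dosing is on Day 1, and Protocol 6.5 asks participants who stop to keep attending visits to Week 52, so early-termination samples may be few.
- The actual-day windows in SAP Tables 3-3 and 3-4 also put early data under later labels. An ECG from Day 2, for example, counts as Week 26.

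All of this stands and limits the point to descriptive tables and the mean and median plots. It does not remove the bias there, because neither the exclusions nor the discretionary outlier clause reliably catches a relabelled sample.

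A reader might also infer more than the documents support:
- **That the Week 26 ADA endpoint is distorted.** Protocol 6.7.1 and Appendix 2 schedule no ADA sample at early termination, so the rule has no scheduled ADA sample to move.
- **That a draw in the first week, labelled Week 4, is inflated severalfold.** Decline soon after infusion may be faster than the terminal half-lives imply, but the documents give no distribution parameters to size it. If the cause was an incomplete infusion, the incorrect-dose exclusion may already apply.
- **That two- to three-and-a-half-fold errors bear on the 26-week targets.** Those figures belong to Weeks 38 and 52, after ART has resumed, and are reachable only on one of two conflicting protocol wordings.

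**Conclusion.** The point holds as a small, one-directional bias in the by-visit summaries of the two antibodies. Per early-termination participant in a group of 10, the mean rises by at most about 3-4% at a 4-weekly visit and 1-2% at Week 26. The rises of roughly 10-19% at Week 38 and 13-25% at Week 52 are conditional on early-termination sampling after Week 26, on which Protocol 6.5 and 6.7.1 differ.

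These sizes assume terminal mono-exponential decline, the preliminary half-lives in the protocol, and one early-termination participant. With none, there is no effect. AUC, Cmax and half-life are largely unaffected. The SAP does not say whether C26wk follows the nominal visit or the actual time; if nominal, one participant's value could be inflated by up to about 1.18-fold. For LEN the label would still be wrong, but the direction is uncertain.

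It is a minor matter, worth correcting because the bias is systematic and the correction is nearly free.

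**What to change.** In SAP 3.8.2, replace the early-termination exception for PK with: *ET PK samples are assigned to a nominal visit only if drawn within the protocol visit window (±3 days) of that visit and no scheduled sample exists; otherwise they are listed by actual time and used in the noncompartmental analysis, but excluded from by-visit summaries and plots.*

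A draw at the edge of that window is off by at most 2^(3/54) = 1.04-fold for GS-5423 and 2^(3/80) = 1.03-fold for GS-2872. No change is needed for ADA. The sponsor should also reconcile Protocol 6.5 with 6.7.1 on whether an early-termination PK sample is taken after Week 26.

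The cost is one sentence and a date check in programming. A few early-termination values leave the by-visit tables but remain in the listings and the parameter estimates. Sample size and power do not change. If the SAP is already final, its introduction provides for recording the change in the CSR.
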